4.7 Efficacy Assessments

Efficacy will be determined by overall response based on international consensus response criteria (see Appendix G).

4.7.1 Rules for deriving the variable confirmed overall response

The confirmation response is the next valid consecutive response at least 84 days (12 weeks) from initial response. The time of response is the actual date of response, not the end of cycle which includes the response.

In patients whose response commences in later cycles before the end of cycle 8 (eg, during cycle 6, 7, or 8), the duration of response will be assessed by ongoing laboratory studies and ongoing visits, performed every 6 weeks. Patients who exhibit a response during cycles 1-8 (or during cycles 9-16), but subsequently demonstrate loss of response before cycle 8 is completed (or before cycle 16 is completed for patients being re-treated), such individuals will not be re-treated. Retreatment after cycles 1-8 is only applicable to patients who exhibit an ongoing response at the time of completion of cycle 8.

In case report forms/study e-CRFs, the confirmed response will be denoted by a subscript 'c', whereas initial responses or unconfirmed responses (eg, responses not yet lasting 12 weeks) will display the subscript 'uc'. For example, if a Major response is confirmed at 12 weeks (Table 3 below, column 3), it will be denoted as 'Major Response_c' or 'MR_c'; whereas an initial Major Response will be denoted as 'Major Response_{uc}' or 'MR_{uc}'.

Table 3 Acceptable combinations for initial and confirmed response

Initial Response	Response at 12 weeks	Confirmed response level
Major _{uc}	Major _{uc}	Major _c
Major _{uc}	Partial _{uc}	Partial _c
Partial _{uc}	Partial _{uc}	Partial _c
Partial _{uc}	Major _{uc}	Partial _c
Cl _{uc}		Cl _c
Cl _{uc}	Cl _{uc}	Cl _c
Cl _{uc}		Cl _c
Partial _{uc}	Major _{uc}	Cl _c
Major _{uc}	Partial _{uc}	Cl _c
	Cl _{uc}	
	Cl _{uc}	

CI: "Clinical Improvement" per international response criteria

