3.2 Discussion of design

Patients will receive open label SGN-35 at a starting dose of 1.8 mg/kg administered as a single IV infusion as on Day 1 of each 21-day cycle as an outpatient. Patients will be treated for eight 21-day cycles. The best response per international response criteria will be recorded by the end of cycle 8. Because responses must last at least 12 weeks, any clinical improvement (CI), partial response (PR), or CR response that commences by the end of cycle 8, and either persists or evolves into a higher quality response for at least 12 weeks will be counted as a response. Patients who demonstrate a response and subsequently meet criteria for loss of response (LOR) will be permitted to undergo re-staging and re-treatment with up to an additional 8 cycles of SGN-35.

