Ascites or pleural effusions	(1) Symptomatic ascites or pleural effusion requiring medical intervention such as use of diuretics (grade 2), OR (2) ≥ 2 therapeutic paracenteses or thoracenteses at least 28 d apart over 12 wk prior to study entry (grade 3), and one of the procedures is performed during the 6 wk prior to drug start	(1) Complete resolution of symptomatic ascites or pleural effusion* AND no longer in need of diuretic(s) for ≥ 12 wk, OR (2) No therapeutic paracentesis or thoracentesis for ≥ 12 wk
Liver function abnormalities	\geq Grade 2 abnormalities in direct bilirubin, AST, ALT, or AP† in the presence of ascites, and/or clinically-relevant portal hypertension, and/or liver MC infiltration that is biopsy-proven or other causes for abnormal liver function are not identified	Reversion of 1 or more liver function tests to normal range for ≥ 12 wk
Hypoalbuminemia	\geq Grade 2 hypoalbuminemia (< 3.0 g/dL)	Reversion of albumin to normal range for ≥ 12 wk
Symptomatic marked splenomegaly	Symptomatic marked splenomegaly: a spleen that is palpable > 5 cm below the left costal margin and the patient endorses symptoms of discomfort and/or early satiety	$\geq 50\%$ reduction in palpable splenomegaly and no endorsement of discomfort and/or early satiety for ≥ 12 wk (3D computed tomography/magnetic resonance imaging evaluation may also be undertaken.)
Hematologic		
ANC	Baseline grade ≥ 3 ANC ($< 1 \times 10^9/L$)	A minimum 100% increase in the ANC and an ANC of at least $0.5 \times 10^9/L$ for ≥ 12 wk
Anemia (transfusion-independent)	Grade ≥ 2 anemia (Hb < 10 g/dL)	An increase in Hb level of at least 2 g/dL that is maintained for ≥ 12 wk
Anemia (transfusion-dependent)	Transfusion of a minimum of 6 units of PRBC in the 12 wk before the start of treatment with the most recent transfusion occurring in the previous 4 wk. RBC transfusions are only considered as part of the baseline criteria if they are administered for an Hb level ≤ 8.5 g/dL and not associated with bleeding, hemolysis, or therapy	Transfusion independence for ≥ 12 wk and maintenance of a minimal Hb level of 8.5 g/dL at the end of the 12 wk period of response duration
Thrombocytopenia (transfusion-independent)	Grade ≥ 2 thrombocytopenia ($< 75 \times 10^9/L$)	A minimum 100% increase in the platelet count and an absolute platelet count increase of at least $50 \times 10^9/L$ and no need for platelet transfusions for ≥ 12 wk

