APPENDIX G Contd.:

APPENDIX G: WG-MRT-ECNM consensus response criteria for patients with ASM, MCL, and SM associated with a myeloid neoplasm

Complete remission (CR)*

Requires all 4 criteria and response duration must be ≥ 12 wk

No presence of compact neoplastic mast cell aggregates in the BM or other biopsied extracutaneous organ

Serum tryptase level < 20 ng/mL†

Peripheral blood count remission defined as ANC $\geq 1 \times 10^9/L$ with normal differential, Hb level ≥ 11 g/dL, and platelet count $\geq 100 \times 10^9/L$

Complete resolution of palpable hepatosplenomegaly and all biopsy-proven or suspected SM-related organ damage (CI findings)‡

Partial remission (PR)*

Requires all 3 criteria and response duration must be ≥ 12 wk, in the absence of both CR and progressive disease (PD)

Reduction by $\geq 50\%$ in neoplastic MCs in the marrow and/or other extracutaneous organ at biopsy demonstrating eligible SM-related organ damage

Reduction of serum tryptase level by $\geq 50\%$ †

Resolution of 1 or more biopsy-proven or suspected SM-related organ damage (CI finding(s)) ‡

Clinical improvement (CI)*

Response duration must be ≥ 12 wk

Requires 1 or more of the nonhematologic and/or hematologic response criteria to be fulfilled (see Table 3) in the absence of both CR/PR assignment or progressive disease (PD)

Stable disease (SD)

Not meeting criteria for CR, PR, CI, or PD

Progressive disease (PD)§

Requires at least 1 element of either criteria 1 or 2 and duration must be ≥ 8 wk

(1) For patients with baseline grade 2 nonhematologic organ damage: a) worsening by 1 grade, AND b) minimum 100% increase (doubling) of laboratory abnormality.

For patients with baseline \geq grade 2 albumin: (a) worsening by 1 grade, AND (b) decrease by ≥ 0.5 g/dL.

For patients with baseline \geq grade 3 nonhematologic organ damage: minimum 100% increase (doubling) of laboratory abnormality.

For patients with baseline \geq grade 2 transfusion-independent anemia or thrombocytopenia: New transfusion dependence of ≥ 4 units of RBCs or platelets at 8 wk.

For patients with baseline transfusion-dependent anemia or thrombocytopenia: $\geq 100\%$ increase in the average transfusion frequency for an 8-wk period compared with the 12-wk pretreatment period

For patients with baseline grade \geq grade 3 neutropenia: (a) $> 50\%$ decrease in neutrophil count, AND (b) absolute decrease of neutrophil count of $\geq 250/mm^3$, AND c) grade 4

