(2) Development of at least 10-cm palpable symptomatic splenomegaly for a baseline spleen size of not palpable or ≤ 5 cm, OR if baseline symptomatic splenomegaly is > 5 cm, a $> 50\%$ worsening and development of at least 10 cm of palpable symptomatic splenomegaly compared with the baseline value.¶

Loss of response (LOR)

Loss of a documented CR, PR, or CI that must be for ≥ 8 wk. Downgrading of CR to PR or PR to CI is considered as such but is not considered as loss of response unless CI is also lost for a minimum of 8 wk. The baseline value for LOR is the pretreatment measurement(s) and not the nadir values during response.

Guidelines for adjudicating response are as follows: (1) Only disease-related \geq grade 2 organ damage is evaluable as a primary endpoint in clinical trials. (2) Response adjudications of CR, PR, SD, PD, and LOR should only be applied to these \geq grade 2 organ damage findings in the context of trials. (3) Disease status at the time of patient removal from the study singularly relates to the updated status of initial \geq grade 2 organ damage finding(s). (4) Exclusion of drug-related toxicity and/or other clinical issues (eg, gastrointestinal tract bleeding in the case of worsening anemia/transfusion-dependence) should be undertaken before assigning the designation PD or LOR in a patient with worsening of baseline \geq grade 2 organ damage.

*Responses that are not maintained or confirmed for a period of at least 12 wk do not fulfill criteria for CR, PR, or CI; however, both maintained and unmaintained (< 12 -wk duration) responses in organ damage should be recorded to determine median duration of response.

†Only valid as a response criterion if the pretreatment serum tryptase level is ≥ 40 ng/mL.

‡Biopsy of organ(s) in addition to the BM to evaluate for SM-related organ damage may be considered.

§Preservation of at least one CI finding permits a patient to maintain the response of 'CI' if 1 or more CI findings are lost but none meet criteria for progressive disease (PD). However, if 1 or more of the CI findings become PD, then the CI finding assignment is lost and the patient meets criteria for PD. The baseline value for evaluating PD is the pretreatment measurement(s). The PD findings must be considered related to the underlying disease and not to other clinical factors. Progression of an underlying chronic myeloid neoplasm to AML is also considered PD in the setting of clinical trials.

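### Section 4.7.1 confirms a response from two overall categories 84 days apart, without tying them to the same organ finding or to the assessments in between, while Section 3.2 and Appendix G require 12 weeks' persistence.

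*Combined protocol and SAP*

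**What the plan says.** The primary endpoint is the overall response rate: complete remission, partial remission or clinical improvement (CI). Section 4.7 sets the standard: "Efficacy will be determined by overall response based on international consensus response criteria (see Appendix G".

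The duration requirement appears in three places.

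- **Section 3.2.** Onset must fall no later than the close of cycle 8. A response that then "either persists or evolves into a higher quality response for at least 12 weeks will be counted as a response".
- **Section 4.7.1.** "The confirmation response is the next valid consecutive response at least 84 days (12 weeks) from initial response". Table 3 maps an initial category and a category at 12 weeks to a confirmed category. The section also describes "initial responses or unconfirmed responses (eg, responses not yet lasting 12 weeks") and says that, for late responders, "the duration of response will be assessed by ongoing laboratory studies and ongoing visits, performed every 6 weeks".
- **Appendix G.** CI "Requires 1 or more of the nonhematologic and/or hematologic response criteria to be fulfilled", and the 12 weeks are written into each organ criterion. For transfusion-independent anaemia the criterion is "An increase in Hb level of at least 2 g/dL that is maintained for" at least 12 weeks. A footnote adds: "Responses that are not maintained or confirmed for a period of at least 12 wk do not fulfill criteria for CR, PR, or CI".

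Appendix G also lets CI continue while at least one CI finding is preserved, and it recognises loss of response only when the loss lasts at least 8 weeks. Section 4.6.1 schedules response assessment on Day 1 of each 21-day cycle from Cycle 2, then every 6 weeks in follow-up for responders.

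**The concern.** Section 4.7.1 is headed as the derivation rule, so it is what a programmer will code. Two things are missing from its operative sentence and from Table 3.

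1. **No same-finding condition.** CI on haemoglobin at week 3 and CI on albumin at week 15 reads as CI followed by CI, hence confirmed CI, although neither finding lasted 12 weeks.
2. **No role for the assessments in between.** A haemoglobin rise seen at week 3, absent at weeks 6 to 12 and present again at week 15 also reads as CI followed by CI.

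Appendix G would reject the first case. The second does not fit its requirement that the rise be maintained. The rule feeds the counts of 2 of 11 and 5 of 26 in a trial without a control arm. One or two patients classified differently can change the decision, and several CI criteria rest on laboratory values that fluctuate.

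**Working it through.** **Passages side by side.** A response first seen at week 3 (Cycle 2 Day 1) is confirmed at week 15. Weeks 6, 9 and 12 lie between, so three scheduled assessments have no stated role in 4.7.1. A response first seen at week 24 is confirmed at week 36, with one assessment between. Section 3.2 and the Appendix G criteria give those assessments a role, because a finding that is absent at them has not persisted.

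**The plan's own figures.** Inputs from Section 7.8: stop if fewer than 2 of 11 respond, succeed if at least 5 of 26 respond, null rate 10%, alternative 30%.

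- P(stop early) = (1−p)^11 + 11p(1−p)^10. At p = 0.10 this is 0.3138 + 0.3836 = 0.697 (stated 70%). At p = 0.30 it is 0.113 (stated 11%).
- P(pass) = Σ over x = 2 to 11 of Bin(x; 11, p) × P[Bin(15, p) ≥ 5 − x]. At p = 0.10 this is 8.65% (stated 8.7%). At p = 0.30 it is 85.2% (stated 85%).

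The design reproduces. The same formula shows how steeply P(pass) rises with the null rate:

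| Null response rate | P(pass) |
|---|---|
| 5% | 0.6% |
| 9% | 6.1% |
| 10% | 8.65% |
| 12% | 15.3% |
| 15% | 28.2% |
| 20% | 51.9% |

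**False confirmed responses with an inert drug.** The documents give no per-visit rate of chance response, so everything here is assumed. Visits fall every 3 weeks to week 24, then at weeks 30 and 36. Onset is allowed to week 24. Each eligible finding meets its threshold by chance at a fraction q of visits. The latent between-patient correlation is 0.3 to 0.5 and the serial correlation is 0.3 to 0.6 per 3 weeks. The two-point rule needs any finding at onset and any finding at the first visit at least 12 weeks later. The every-visit rule needs one finding throughout.

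| q | Eligible findings | Two-point rule | Every-visit rule |
|---|---|---|---|
| 2% | one | 1–2% | under 1% |
| 2% | two | 2–3% | about 1% or less |
| 5% | one | 4–5% | about 2% or less |
| 5% | two | 9–11% | 1–4% |
| 10% | one | 10–12% | 2–5% |
| 10% | two | 22–24% | 3–10% |

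**Effect on the decision, if chance responses are the whole null rate.** P(pass) stays under 1% at q = 2%, and at q = 5% with one finding. It is about 6–12% at q = 5% with two findings, and about 9–15% at q = 10% with one. At q = 10% with two findings it is about 62–68%, against 0.1–8.5% under the every-visit rule. If only the first-ever response may start the clock, the 22–24% in that last setting falls to about 16%.

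**Effect on the decision, if chance responses come on top of a separate 10%.** Then p = 0.10 + 0.90f, where f is the false-response rate. This was run for one finding, with serial correlation 0 to 0.8, no between-patient term and visits to week 48. For example, f = 4.0% gives p = 0.136 and P(pass) of about 22%.

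| q | P(pass), two-point | P(pass), every visit |
|---|---|---|
| 2% | 9.5–12% | 8.7–9.9% |
| 5% | 15–22% | 8.7–14% |
| 10% | 35–47% | 9–26% |

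**The case against.** The strongest reply is that the plan already requires continuity. Section 4.7 makes Appendix G the governing standard, and Appendix G fixes 12 weeks to each finding. Section 4.7.1 itself says *consecutive*, describes unconfirmed responses as not yet having lasted 12 weeks, and follows late responders' duration at 6-weekly visits. This carries weight on intent. A reader might infer that the plan deliberately accepts two isolated readings, and the documents do not support that. A reader might also infer that a failure at week 15 followed by a response at week 24 would confirm. The word *consecutive* and Table 3's 12-week column largely exclude it. What the reply does not supply is an algorithm: *consecutive* is undefined, and nothing in 4.7.1 addresses a change of finding.

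Appendix G is not a clean opposite either. It says maintained *or confirmed*, allows CI to continue on one preserved finding, and recognises a loss only after 8 weeks. It therefore leaves a brief lapse unsettled, which is a reason to state a rule and also a reason not to impose the strictest one without thought.

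The magnitude is open to challenge, and that objection stands. The rates are assumed. Eligibility needs only one organ finding. Transfusion independence and freedom from paracentesis are defined over an interval, so a visit-level model does not fit them. The 10% null may already allow for spontaneous fluctuation.

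The CI rows of Table 3 are partly broken in the available text. The point rests only on the legible row in which CI is followed by CI, and on the operative sentence.

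**Conclusion.** The point holds as an internal inconsistency in the rule that produces the primary endpoint. A literal derivation under 4.7.1 and Table 3 can count a patient whom Section 3.2 and Appendix G would not, most clearly when the responding finding changes between the two time points.

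Two-point confirmation admits more chance responses than an every-visit rule in all the settings tried, but the size is not known. Over assumed per-visit rates of 2–10%, false responses run from about 1% to 12% with one eligible finding and from about 2% to 24% with two. A reader might take the 62–68% pass probability as the trial's false-positive risk. The documents do not support that: it arises only with two eligible findings and chance response at 10% of visits. With one finding, or at lower rates, the two-point false-response rate is about 12% or less, close to or below the 10% null. If chance responses add to a separate 10%, the excess over 8.7% is small at 2% of visits and material from about 5%. If the 10% already includes them, there is less inflation or none. The documents also give no basis for assuming that CI will be the commonest response.

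**What to change.** Reconcile 4.7.1 and Table 3 with Section 3.2 and Appendix G.

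- **CI.** State that it is confirmed only when the same Appendix G finding is met at the initial assessment, at the available scheduled assessments of that finding in between, and at the first scheduled assessment at least 84 days later, with no intervening progressive disease. Where several findings respond, at least one must be preserved throughout. A response on a different finding does not confirm.
- **Complete and partial remission.** Apply the continuity check only to components assessed at each visit. Judge the marrow at its scheduled time points, since on-treatment marrow is planned only at the end of cycles 4 and 8.
- **Lapses.** State how a missing visit and an isolated failing visit are handled, consistently with Appendix G's maintained-or-confirmed wording and its 8-week rule for loss of response.
- **Labels.** While Table 3 is open, map its Major category to an Appendix G category, since Appendix G has none of that name.

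The cost is a paragraph of protocol text and some derivation programming on data already collected. The observed response rate may fall somewhat, and power falls if isolated failures are treated strictly. As an illustration, suppose a true responder independently fails each of four later visits with probability 5% (assumed). Then 30% × 0.95^4 = 24.4%, and power drops from 85% to about 70%. At 2% the rate is 30% × 0.98^4 = 27.7% and power is about 80%. The rule for isolated failures should therefore be chosen with this loss in view, and fixed before responses are counted.

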4.6 Visit schedule and assessments

4.6.1 Visit and assessment schedule (see next page)

Evaluations

Pretreatment (Screening)

- Complete medical history including transfusion history in prior 12 weeks
- Prior and current medication list
- Physical exam with spleen measurement
- ECOG performance status
- Vital signs (temperature, heart rate, breathing rate, blood pressure, height, weight)
- 12 lead ECG

A study of brentuximab vedotin (SGN-35) in CD30-positive systemic mastocytosis with or without an associated hematological clonal non-mast cell lineage disease (AHNMD)

- Magnetic resonance imaging (MRI) or computed tomography (CT) scan of the abdomen/pelvis with and without contrast including 3D spleen and liver volumes
- Bone marrow aspirate and biopsy with cytogenetics, flow cytometry, *KIT* mutation status
- Chest x-ray (2 views PA and lateral)
- MPN-SAF modified for mast cell symptoms
- Hematology, chemistries/liver function tests, serum tryptase, PT, PTT (**Please refer to section 4.8.1 for detailed lab evaluations**)
- Pregnancy test (women of child bearing potential)

Day 1 of Cycles 1 to 8 (+/- 3 days):

- Evaluate for adverse events
- Interval medical history including transfusion history
- Physical exam, including measurement of your spleen, weight, and vital signs
- Current medications
- ECOG performance status
- MPN-SAF modified for mast cell symptoms
- Hematology, chemistries/liver function tests (with phosphorus on Cycle 1 Day 1 only), serum tryptase, PT, PTT (**Please refer to section 4.8.1 for detailed lab evaluations**)
- Pregnancy test (women of child bearing potential)
- Drug infusion
- Response assessment per IWG-MRT-ECNM criteria (starts Cycle 2 Day 1)

For Cycle 5 Day 1 (End of cycle 4) also need to complete the following:

- MRI or a CT scan of the abdomen/pelvis with and without contrast including 3D spleen and liver volumes
- Chest X-ray-2 views PA and lateral (only if disease-related finding(s) were found at baseline)
- Bone marrow aspirate and biopsy with cytogenetics, flow cytometry, *KIT* mutation status

Phosphorus will be additionally done on Cycle 1 Day 1; Cycle 1 Day 3; and Cycle 1 Day 8 only, for complete evaluation of tumor lysis.

Day 3 of Cycle 1

- Serum chemistries/liver function tests and phosphorus
- Evaluate for adverse events

Days 8 and 15 of Cycle 1 (+/- 3 days)

- Evaluate for adverse events
- Hematology
- Serum chemistries/liver function tests and phosphorus

Day 10 of Cycles 2-8 (+/- 3 days)

- Hematology

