- Evaluate for adverse events

End-of-Treatment (End of Cycle 8) Visit

- Evaluate for adverse events
- Interval medical history including transfusion history
- Current medications
- Physical exam, including measurement of spleen, weight, and vital signs
- ECOG performance Status
- MPN-SAF modified for mast cell symptoms
- Hematology, chemistries/liver function tests, serum tryptase, PT, PTT (**Please refer to section 4.8.1 for detailed lab evaluations**)
- Pregnancy test (women of child bearing potential)
- MRI or CT of abdomen/pelvis with and without contrast including 3D spleen and liver volumes
- Chest x-ray 2 views - PA and lateral (only if disease related finding(s) were found at baseline)
- Bone marrow aspirate and biopsy with cytogenetics, flow cytometry, *KIT* mutation status
- Response assessment per IWG-MRT-ECNM criteria Drug Accountability

End of Study (EOS) Visit - if no response to the study drug after 8 cycles of treatment, one follow-up visit about 30 days after the end-of-treatment visit

- Evaluate for adverse events

- Interval medical history including transfusion history
- Current medications
- Physical exam, including measurement of spleen, weight, and vital signs
- ECOG performance status
- MPN-SAF modified for mast cell symptoms
- Hematology, chemistries/liver function tests, serum tryptase (**Please refer to Section 4.8.1 for detailed lab evaluations**)
- Pregnancy Test (women of child bearing potential)
- Response assessment per IWG-MRT-ECNM criteria

Follow-up visits - if patient did exhibit a response to the study drug after 8 cycles of treatment according to protocol response criteria, follow-up visits and labs every 6 weeks until 48 weeks from beginning of treatment will occur, then every 12 weeks.

- Evaluate for adverse events
- Interval medical history including transfusion history
- Current medications
- Physical exam, including measurement of spleen, weight, and vital signs
- ECOG performance status
- MPN-SAF modified for mast cell symptoms
- Hematology, chemistries/liver function tests, serum tryptase (**Please refer to Section 4.8.1 for detailed lab evaluations**)
- Bone Marrow aspirate and biopsy, cytogenetics, flow cytometry, *KIT* mutation status (at week 48, then every 24 weeks)
- MRI or CT of abdomen/pelvis with and without contrast including 3D spleen and liver volumes (at week 48, then every 24 weeks)
- Drug accountability
- Response assessment per IWG-MRT-ECNM criteria

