- ECOG performance Status
- MPN-SAF modified for mast cell symptoms
- Hematology, chemistries/liver function tests, serum tryptase (**Please refer to section 4.8.1 for detailed lab evaluations**)
- Bone Marrow aspirate and biopsy, cytogenetics, flow cytometry, *KIT* mutation status (at week 48 from day 1 of re-treatment, then every 24 weeks)
- MRI or CT of abdomen/pelvis with and without contrast including 3D spleen and liver volumes (at week 48 from re-treatment, then every 24 weeks)
- Response assessment per IWG-MRT-ECNM criteria

There will not be any additional treatments after completion of the drug infusion at start of cycle 16. Patient will come for follow up visits per the schedule above as long as they show response. At the time of loss of response, patient will have an end of study visit (with the same assessments as at the end of study (EOS) visit for patients with no response at end of cycle 8 or 16) and will be taken off the study.

Long-term survival:

All patients will be followed every 6 months for survival until study closure or death of the patient.

Table 2. Visit and Assessment Schedule

	Screen	Assessments within +/- 3 days						End of Treatment (EOT) (@ completion of 8 cycles of therapy)	Day +30 after EOT for non-responders (g)	Maintenance labs and visits after 8 cycles for ongoing responders (h)	Re-Staging for pts who exhibit loss of response (LOR)	Re-Treatment Cycles 9-16 ^(a) for pts who exhibit loss of response (LOR)	Long Term Survival ^(j)
		Cycle 1			Cycle 2-8								
Evaluation	Day -28 to Day -1	Day 1 ^(b)	Day 3 (can be local)	Day 8 (can be local)	Day 15 (can be local)	Day 1	Day 10 (can be local)	(EOT)	(EOS)	Labs and visits q 6 weeks up to week 48; then q 12 weeks	Day -21 to Day -1	Repeat schedule of original cycles 1, 2-8 and EOT (except PT, PTT)	
Informed consent/eligibility criteria	X												
Complete medical history	X												
Interval medical history		X				X		X	X	X	X		
Prior and concomitant medications	X	X				X		X	X	X	X		
Transfusion history in prior 12 weeks	X	X				X		X	X	X	X		
Vital signs, physical exam, body weight, height ⁽ⁱ⁾	X ⁽ⁱ⁾	X				X		X	X	X	X		
ECOG performance status	X	X				X		X	X	X	X		
MPN-SAF, QOL questionnaires	X	X				X		X	X	X	X		
12-lead ECG	X												
Hematology ^(c)	X	X		X	X	X	X	X	X	X	X		
Serum chemistries/liver function tests ^(c)	X	X	X	X	X	X		X	X	X	X		
Serum tryptase level	X	X				X		X	X	X	X		
PT and PTT	X	X				X		X					
Pregnancy test	X	X				X		X	X		X		

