- d If disease-related findings are found on chest x-ray (2 views PA and lateral) (eg, pleural effusion), then an x-ray will be performed at the end of cycles 4 and 8 or EOT, whichever comes first, and at the time of progressive disease or loss of response (LOR). Chest X-ray (2 views-PA and lateral) will also be performed at the time of re-staging. If disease-related findings are found on chest x-ray (eg, pleural effusion) at the time of re-staging, then an x-ray will be performed at the end of cycles 12 and 16 or EOT, whichever comes first, and at the time of progressive disease or loss of response (LOR). Interval chest x-rays can be performed at the discretion of the investigator.
- e Besides screening, marrows will be performed at the end of cycles 4 and 8 or EOT, whichever comes first, and at the time of progressive disease or loss of response (LOR). A repeat bone marrow aspirate and biopsy should be performed at the end of week 48 and every 6 months thereafter in ongoing responders. Please refer to section 4.9 Central Histopathology Review for items required with bone marrow biopsy and aspiration.
- f MRI (or CT scan) abdomen/pelvis with and without contrast including 3-D spleen and liver volumes will be obtained at screening, at the end of cycle 4, and at the end of cycle 8 or EOT, whichever comes first, and at the time of progressive disease or loss of response (LOR). Interval MRI or CT scans can be performed at the discretion of the investigator. A repeat MRI or CT should be performed at the end of week 48 and every 6 months thereafter in ongoing responders.
- g A visit on day +30 will be conducted after the EOT visit for follow-up for non-responders. This will be end of study visit (EOS)
- h After 8 cycles of therapy are completed, labs and visits with the trial site every 6 weeks up to week 48; then every 12 weeks.
- i Height is to be obtained only at screening.
- j Long Term Survival: every 6 months after end of study visit until study closure or death of the patient.

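### The 84-day confirmation rule equals the planned gap between the two on-treatment marrows, so ordinary visit windows can defer, and sometimes lose, marrow confirmation of a CR or PR

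*Combined protocol and SAP*

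**What the plan says.** Section 4.7.1 sets the rule: "The confirmation response is the next valid consecutive response at least 84 days (12 weeks) from initial response". The same section dates a response by the day it actually occurred, not by the end of the cycle. It gives no tolerance for visit windows and no upper limit on the interval.

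The schedule comes from three places.

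- Section 3.2: "Patients will be treated for eight 21-day cycles".
- Table 2, footnote e: "Besides screening, marrows will be performed at the end of cycles 4 and 8 or EOT, whichever comes first". Marrows are also taken at progression or loss of response.
- Section 4.6.1 places the end-of-cycle-4 marrow at the Day 1 visit of cycle 5 ("For Cycle 5 Day 1 (End of cycle 4) also need to complete the following"), and Day 1 visits have a window of three days either side. The second marrow belongs to the "End-of-Treatment (End of Cycle 8) Visit", which has no window in the visit list. Table 2 has a general header, "Assessments within +/- 3 days", but the available text does not show whether it spans the end-of-treatment column.

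After treatment, responders have visits and response assessments every 6 weeks, but marrow only "at week 48, then every 24 weeks".

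In Appendix G, CR and PR each need a marrow or other biopsy element and a duration of at least 12 weeks. PR also needs at least one organ-damage finding to resolve, and CR needs all of them to. CI needs no marrow.

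**The concern.** Four 21-day cycles make 84 days, exactly the minimum that the confirmation rule demands. A first marrow taken a day late, or a second taken a day early, puts the pair under the minimum even though both samples meet the criterion. No further marrow is scheduled for about 24 weeks after end of treatment.

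Section 7.5 tabulates best clinical response and estimates the rates of CR, PR and CI. If a few days of scheduling decide whether a patient is recorded as a confirmed PR or as CI, that split partly reflects the calendar. In a first stage of 11 patients, one reclassification moves a category by 1/11, about 9 percentage points.

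**Working it through.** **Inputs.** Confirmation at least 84 days after the initial response, by actual date (4.7.1). Cycle length 21 days, eight cycles (3.2). First on-treatment marrow at Cycle 5 Day 1, ±3 days; second at end of cycle 8; next at week 48 (4.6.1 and Table 2, footnote e). Decision rules: at least 2 of 11, then at least 5 of 26, with response rates of 10% and 30% (7.8).

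**The plan's own figures.** Section 7.8 gives alpha 8.7%, power 85%, and early stopping of 70% and 11%. Exact binomial calculation reproduces them:

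- Stopping at a 10% rate: 0.9^11 + 11 × 0.1 × 0.9^10 = 0.314 + 0.384 = 0.697.
- Stopping at a 30% rate: 0.7^11 + 11 × 0.3 × 0.7^10 = 0.020 + 0.093 = 0.113.
- P(continue, then at least 5 of 26): 0.0865 at 10% and 0.8516 at 30%.

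The design is correctly calculated. The issue lies in the dates.

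**Nominal gap.** Cycle 5 Day 1 is day 4 × 21 + 1 = 85. Section 4.6.1 equates that day with the end of cycle 4, so the matching end of cycle 8 is day 8 × 21 + 1 = 169, giving 169 − 85 = 84. If the visit is held on the last day of cycle 8, day 168, the gap is 83.

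**Effect of the windows.** Gap = nominal gap + shift of the second visit − shift of the first. Each shift takes the values −3 to +3 with equal probability, independently, and no cycle is delayed. These are assumptions; the documents give no distribution of visit dates.

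| Nominal gap | Window on end of treatment | Range of gap (days) | Pairs under 84 days |
|---|---|---|---|
| 84 | none | 81–87 | 3/7 = 42.9% |
| 84 | ±3 | 78–90 | 21/49 = 42.9% |
| 83 | none | 80–86 | 4/7 = 57.1% |
| 83 | ±3 | 77–89 | 28/49 = 57.1% |

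The largest shortfall at a nominal 84 days is 3 days, or 6 if the window also covers end of treatment. It is one day more if that visit is on day 168. Whether the Table 2 header covers end of treatment does not change the percentage.

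**When the next marrow comes.** The end of week 48 is day 48 × 7 = 336. That is 336 − 85 = 251 days after Cycle 5 Day 1 and 336 − 169 = 167 days after end of treatment. The first 6-weekly visit is about 84 + 42 = 126 days after Cycle 5 Day 1. It includes a response assessment but no marrow.

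**Effect on the primary test.** CR, PR and CI count alike (2.3.1, 7.5). A patient recorded as CI instead of PR stays a responder, so power stays at 85.2%.

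**The case against.** The strongest answer is that a short gap only defers confirmation. The rule has no upper limit, so a later assessment can confirm, and week 48 supplies a marrow if one is required. This stands. It does not cover a response that lasts beyond 12 weeks but ends before week 48: the marrow taken at loss of response cannot confirm a CR or PR.

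The second answer is that no passage requires a marrow at both ends of the interval. Section 3.2 asks that a response persist for 12 weeks, response is assessed each cycle from cycle 2 although marrows are less frequent, and for responses starting late in treatment Section 4.7.1 uses laboratory studies and 6-weekly visits to judge duration. This has force. But Section 4.7.1 does not say whether that method covers the marrow element, or responses first seen at Cycle 5 Day 1.

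The percentages are also open to challenge. If later cycles run from the actual infusion date, a late Cycle 5 Day 1 moves end of treatment with it and the gap stays near nominal. Delays of up to 30 days (4.2.5), where they follow Cycle 5 Day 1, lengthen it. The figures apply only to undelayed patients whose CR or PR is dated from the Cycle 5 Day 1 marrow.

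A reader might infer two stronger conclusions.

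- *That the primary endpoint or the Simon rules are at risk.* Power would fall only if short-gap patients were scored as non-responders. If 10%, 25%, 50% or 100% of true responders depended on this gap (assumed shares) and 3/7 of them were lost, power would be 82.4%, 77.4%, 66.9% or 38.4%. The documents do not support that scoring. Every patient enters with eligible organ damage (3.3.2), and a CR or PR includes resolution of such a finding, largely followed by laboratory tests and examination.
- *That scans raise the same problem.* Appendix G judges spleen response by palpation with 3D imaging optional, ascites and effusion have a criterion based on procedures alone, and Table 2, footnote f allows interval scans at discretion.

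**Conclusion.** The point holds for the marrow element of CR and PR. The planned gap has no slack against a rule with no tolerance; that follows from the documents' own dates. A patient whose marrow element is met at both on-treatment samples can miss the interval by up to 3 days at a nominal 84-day gap, up to 6 if the window covers end of treatment, and one day more if that visit is on day 168. The 43% (57%) frequency rests on independent, uniform visit dates and no delays, so it shows the scale and is not a forecast.

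Confirmation by marrow is then deferred to week 48, and lost if the response ends before that. What is exposed is the CR/PR versus CI split and the best-response table in Section 7.5. This is worth correcting because the remedy is nearly free and an ambiguity would otherwise be settled after the data are seen.

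**What to change.** Make one of these two changes.

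- In Table 2, footnote e, schedule the end-of-cycle-8 marrow no earlier than 84 days after the actual date of the end-of-cycle-4 marrow, with a window of 0 to +7 days.
- Or state in Section 4.7.1 that the confirmation interval allows for the visit windows. With end of treatment on day 169, the minimum would be 81 days if only Cycle 5 Day 1 has a window, or 78 if both visits do. With day 168 these become 80 and 77.

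In either case, state in Section 4.7.1 whether the last marrow result carries forward when duration is confirmed at the 6-weekly visits, and whether this applies to responses first seen at Cycle 5 Day 1 as well as to later ones.

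The cost is wording. The first option may move the end-of-treatment marrow a few days later. The second accepts a minimum slightly under 84 days, while Appendix G asks for at least 12 weeks, so the allowance should be stated openly. Neither adds a procedure or changes the Simon design.
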